6. ANALYSIS POPULATIONS

Reference Section 9.2 Protocol VMDN-003-2 for the complete definitions of the populations for analysis. The sections below align with the definitions in the protocol.

6.1. Intent-to-Treat (ITT) Population

The intent-to-treat (ITT) population includes all participants who are randomized. The ITT population will be the primary population used for the efficacy analyses.

All baseline characteristics will be summarized based on the ITT population. The primary analyses of the primary and secondary efficacy endpoints will be based on the ITT population.

Participants in the ITT population will be analyzed according to the randomized treatment assignment, regardless of the actual treatment administered.

6.2. Safety Population

The safety population includes all participants who are randomized and receive at least one study drug injection. The safety population will be used for the safety analyses.

Participants will be analyzed by the actual treatment administered, not according to their randomization assignment. Participants treated with any Engensis dose will be grouped in the Engensis group; participants never treated with any Engensis will be grouped in the Placebo group.

6.3. Modified Intent-to-Treat (mITT) Population

The modified ITT (mITT) population includes all participants that meet the following:

- Underwent (any) injections
- Correctly completed for at least 5 out of 7 days the BPI-DPN eDiary at baseline and the 6-month follow-up

Participants will be grouped based on the randomly assigned treatments, not the actual treatment received. The mITT population will be used in the sensitivity analyses for the primary and secondary efficacy endpoints.

6.4. Per Protocol (PP) Populations

The Per Protocol population is a subset of mITT. It includes all mITT participants who meet all of the following criteria:

- The participant meets major protocol eligibility criteria determined by Clinical Data Review Committee (CDRC) prior to database lock and breaking the randomization codes.
- The participant received all injections based on the randomized treatments and had a Day 180 Visit, including a 7-day ADPS.

The CDRC, which is masked to the treatment information of each participant, may determine additional criteria, if any, before unblinding the randomization code.

The PP population will be used in the sensitivity analyses for the primary and secondary efficacy endpoints.

VMDN-003-2 Version 7.0

6.5. Subgroup Analysis Subsets

The subgroup analyses will be exploratory in nature and will be conducted in the ITT population. The primary and secondary efficacy endpoints will be evaluated based on the categories of the covariates described in Section 4.6 as well as the stratification factor. These subgroups that will be re-examined and may be recategorized or eliminated due to small sample size (if there are <10% of participants within each subgroup) before unblinding for analysis. For example, if <10% of overall participants are \geq 65 years, then analyses for this subgroup will not be performed. The treatment by subgroup interaction will be examined and tested as described in Section 8.4.5.

7. GENERAL PRINCIPLES OF DATA HANDLING

Data screening will be conducted in a blinded fashion periodically during the conduct of the study. The objective of the data screening is to assess the quantity, quality, and statistical characteristics of the data relative to the requirements of the planned analyses. The designated Contract Research Organization (CRO) will be responsible for data cleaning and dictionary coding of AEs, medical history, and medications. Any questionable values or situations will be reported to the CDRC for final review and confirmation.

7.1. Baseline Definition

Unless specified otherwise, the baseline value for each variable is the value recorded at the last visit on or before start of dosing.

For the pain scores from the BPI-DPN eDiary, the baseline value is the Average Daily Pain Score prior to the Day 0 visit.

Note that, for eligibility, the mean of Average Daily Pain Scores of the BPI-DPN eDiary should be ≥ 4 during the 7 days prior to Day 0. For the Average Daily Pain Score calculation, at least five (5) days need to have the available scores.

7.2. Visit Windows

Data at each scheduled follow-up visit will be analyzed according to the nominal visit identified on the data record.

In case of multiple different visits with the same nominal visit designation, the visit with the visit date closest to the target days of each protocol-specified visit schedule will be used for the efficacy analyses. For visits with the same distance to the target days, the later nominal visit record will be used. Data from all visits will be provided in the data listings.

If a subject fails to complete a study visit but provides necessary eDiary data during the time period expected for that visit (i.e. based on study day relative to the date of the first dose in VMDN-003-2), those eDiary data will be used to derive applicable endpoints. Day 90 endpoint would be derived by the eDiaries recorded 7 days up to 90 days from the date of first dose. Also, Day 104 endpoint would be derived by the eDiaries recorded 7 days up to 104 days from the date of first dose. Similarly, Day 180 endpoint would be derived by the eDiaries recorded 7 days up to 180 days from the date of first dose. Otherwise, if subject completes study visit, then date of visit will be used to derive applicable endpoints.

7.3. Unmasking of Randomization Codes

Following database lock, the randomization code will be unmasked to the project team. The randomization code will be unmasked to the Data Safety Monitoring Board (DSMB; Section 7.5) members and the CRO that will prepare the unmasking summary tables for the DSMB meetings. However, to prevent bias, the unmasking detailed data summaries will not be shared with the sponsor management team, the CDRC, or the team that is monitoring the clinical data collection. The participant and study personnel, including core lab, principal investigator, co-investigators, study coordinators, study monitors and study director will remain blinded to individual data and group results until all data has been entered into the database and the database is locked.

7.4. Multiplicity Adjustment

To control the family-wise type 1 error rate at 0.05 for multiplicity across the primary and secondary

endpoints, a hierarchical testing strategy³ will be used. The hierarchical testing strategy starts with the primary endpoint followed by sequential testing of the secondary endpoints. The statistical significance will be evaluated in the following order: If a statistical significance at the 0.05 level (2-sided) is shown for the first ranking order, then the next endpoint in the immediate subsequent order will be evaluated; evaluation of subsequent endpoints will continue in the same manner. If no statistical significance is shown at 0.05 level at any endpoint, then the endpoint and all subsequent endpoints will not be considered statistically significant, regardless of their p-values.

The hierarchical testing order follows:

- 1. Change in the means of the Worst Pain Scores from the BPI-DPN from the 7 days prior to the Day 0 Visit to the 7 days prior to the Day 180 Visit for Engensis compared to Placebo
- Proportion of Responders (≥ 50% reduction in the means of ADPSs from the BPI-DPN)
 from the 7 days prior to the Day 0 Visit to the 7 days prior to the Day 180 Visit for
 Engensis compared to Placebo

The p-values for other secondary and exploratory endpoints will be used for informative or supportive purposes only. Therefore, there will be no further adjustment for multiple tests.

7.5. Data Safety Monitoring Board

In addition to the interim assessment of the sample size by the Independent Data Monitoring Committee (IDMC), a separate independent DSMB will periodically review a limited set of unblinded tables and/or listings, including all reported AEs. The objectives of the DSMB meetings are to review the safety outcomes of the study and provide guidance to the study sponsor regarding the safety of the Engensis. The data analyses for the DSMB meetings will be directly provided to the DSMB members and no data will be released to the study sponsor and blinded designees. There will be no adjustment for multiple testing due to the DSMB data review. The DSMB may be asked to review and provide guidance regarding protocol deviations that may affect the determination of the PP populations. Further details of DSMB responsibilities are included in the DSMB Charter.

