#### 9.2.4. Per Protocol (PP) Population

The Per Protocol population is a subset of mITT. It includes all mITT Participants who meet all the following criteria:

- The Participant met major protocol eligibility criteria determined by Clinical Data Review Committee (CDRC) prior to database lock and breaking the randomization codes.
- The Participant received all injections based on the randomized treatments and had a Day 180 Visit, including a 7-day ADPS.

Additional criteria, if any, will be established before unblinding the randomization code by the independent CDRC that is masked to the treatment information of each Participant.

The PP population will be used in the sensitivity analyses for the primary and secondary efficacy endpoints.

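### SAP 7.5 lets the DSMB be asked for guidance on deviations affecting the per-protocol set, with no limit to masked material, although SAP 7.3 unmasks its members and SAP 6.4 gives per-protocol judgements to a masked committee

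*SAP*

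**What the plan says.** SAP 7.5 describes a board with safety objectives that periodically reviews unblinded tables or listings. It then adds: "The DSMB may be asked to review and provide guidance regarding protocol deviations that may affect the determination of the PP populations". It does not say who asks, who receives the guidance, or what material the board uses. The next sentence refers to the DSMB Charter for further details.

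SAP 7.3 says "The randomization code will be unmasked to the Data Safety Monitoring Board" members, and also to the CRO that prepares their tables. The same section sets a barrier: "to prevent bias, the unmasking detailed data summaries will not be shared with the sponsor management team, the CDRC" or the clinical data monitoring team.

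SAP 6.4 places per-protocol judgement with a masked body. One criterion is "The participant meets major protocol eligibility criteria determined by Clinical Data Review Committee (CDRC) prior to database lock and breaking the randomization codes". It continues: "The CDRC, which is masked to the treatment information of each participant, may determine additional criteria" before unblinding. Protocol 9.2.4 likewise has additional criteria set before unblinding "by the independent CDRC that is masked to the treatment information of each Participant".

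Both documents use the per-protocol set in sensitivity analyses of the primary and secondary efficacy endpoints. The primary analyses of those endpoints use the ITT population (Protocol 9.2.1, SAP 6.1).

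**The concern.** A per-protocol analysis supports the ITT result only if exclusions were judged without knowledge of treatment. The plan accepts this principle: it masks the CDRC and keeps unmasked summaries from it, expressly to prevent bias. The sentence in SAP 7.5 leaves a side route. Unmasked data may not pass to the CDRC, but advice from people who hold the code may.

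At stake is how much weight agreement between the per-protocol and ITT results can bear. If unmasked members have advised on which deviations matter, that agreement is less persuasive, because the advice behind some exclusions may not have been independent of assignment.

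**Working it through.** No figure in the plan changes with this point, so the check compares passages.

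**1. Is the DSMB unmasked while deviations are being reviewed?** SAP 7.3 dates the project team's unmasking: "Following database lock, the randomization code will be unmasked to the project team". The DSMB sentence carries no such date. Its purpose is the DSMB meetings, which SAP 7.5 says occur periodically. On the SAP's text, members are therefore unmasked during the trial. The protocol is not consistent on the extent:

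| Place | Extent of DSMB unblinding |
|---|---|
| Protocol 1.1 (Synopsis) | Periodic unblinded but noncomparative tables or listings |
| Protocol 6.3.3 | Unblinded SAE narratives at the Chair's request; no unblinded tables or listings unless the Chair asks over a possible safety signal |
| Protocol 10.1.5.1 | Periodic unblinded tables or listings; unblinded narratives at routine meetings |
| SAP 7.3 | Randomization code unmasked to members |
| SAP 7.5 | Periodic unblinded tables or listings |

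Even the narrowest version, Protocol 6.3.3, allows unblinded participant narratives. Per-protocol exclusion is also decided participant by participant.

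**2. Do deviations bear on per-protocol membership?** Yes. SAP 7.5 says so itself, and SAP 8.2 lists major deviations for participants outside the per-protocol populations.

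**3. Is there discretion for advice to influence?** Some. Deciding which eligibility criteria are major, and whether to add criteria, requires judgement. Other conditions are largely factual, such as "The participant received all injections based on the randomized treatments" and having a Day 180 Visit.

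**4. Do the stated safeguards reach advice?**

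| Safeguard | What it blocks |
|---|---|
| SAP 7.3 | Unmasked detailed summaries reaching sponsor management, the CDRC or the data-monitoring team |
| SAP 7.5 | Release of data to the sponsor and blinded designees |
| Protocol 10.1.5.1 | The Chair sharing unblinded information with the sponsor, except where needed for a safety concern |

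Each blocks data or information. None addresses a recommendation on a deviation that reveals no data but was formed with knowledge of assignment.

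**5. Does the protocol provide for this role?** Protocol 10.1.5.1 describes safety review and gives the DSMB no part in defining the per-protocol set. The permission appears only in the SAP.

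**6. Size.** The documents give no expected number of deviations or per-protocol exclusions, so no bias or range can be computed.

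**The case against.** The strongest reply is that advice and decision can coexist. SAP 7.5 says only that the DSMB may be asked, and it transfers no determination. SAP 6.4 does not mention classifying deviations; it names major eligibility criteria and additional criteria, and the masked CDRC must still settle them before lock and code break. The DSMB's stated purpose is safety, no passage shows it efficacy by arm, and the interim sample-size assessment goes to a separate committee. Biased advice would have to work through the discretionary part of the definition and survive a masked decision. The Charter may also limit the role. All of this stands, and it bounds the concern. It does not close the gap, because the SAP states a permission with no masking limit.

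A milder remedy would confine the DSMB's deviation review to masked listings. That is weaker than deletion, because members who hold the code cannot be re-masked.

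A reader might infer that the sponsor could never document the independence of the per-protocol decisions. The documents do not support that. The role may never be used, and a dated CDRC decision before lock, with a record of what the DSMB had been shown, could go some way towards documenting it.

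**Conclusion.** The point holds as a bounded weakness that should be corrected. The SAP permits guidance from unmasked people on matters that feed a definition the plan otherwise keeps masked, and no stated safeguard covers that guidance. If the option is used, the per-protocol sensitivity analyses lose some of their value as evidence of robustness, by an amount that cannot be computed.

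A reader might go further and infer that the DSMB decides per-protocol membership, or that the primary result is compromised. Neither follows: the CDRC keeps the decision, and the primary analyses of the primary and secondary efficacy endpoints are on the ITT population.

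The conclusion assumes that SAP 7.3 means what it says about unmasking DSMB members, and that the Charter does not already confine the role. It also rests on the SAP text supplied. The body of the efficacy-analysis section (SAP 8.4) is not in that text, so the exact weight given to per-protocol results cannot be judged beyond their stated use in sensitivity analyses.

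**What to change.** Delete the sentence from SAP 7.5. State in SAP 6.4 that the masked CDRC alone classifies protocol deviations and settles judgement-based per-protocol membership, from blinded listings, before database lock and code break, and without advice from anyone unmasked. Check that the DSMB Charter agrees.

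As a separate item, reconcile the statements on the extent of DSMB unblinding in Protocol 1.1, 6.3.3 and 10.1.5.1 and SAP 7.3 and 7.5.

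The cost is small: one sentence removed, a short statement added, a Charter check, and aligned wording. The masked CDRC exists, and SAP 7 already sends questionable values or situations from blinded data screening to it, so no new body is needed. The change should be made before any DSMB advice on deviations is sought, since later wording cannot undo advice already given.

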7.6. Handling of Missing and Incomplete Data

Participants may have missing specific data points for a variety of reasons. In general, data may be missing due to a participant's early withdrawal from study, a missed visit, or a clinical parameter not measured at a particular point in time. The general procedures outlined below describe how missing data will be addressed in the analyses.

7.6.1. Missing Pain Scores for the Average Scores from BPI-DPN

The means of the Average Daily Pain Scores (Question 5 from the BPI-DPN) for a visit will be considered as missing if fewer than 5 of 7 days of BPI-DPN eDiary entries are provided. Any missing mean pain score of ADPS will be imputed using the methods described below.

- Multiple Imputation (MI) method:
 - Step 1: Intermittent missing values will first be imputed by treatment group using the Markov Chain Monte Carlo (MCMC) method, resulting in data with a monotone pattern.
 - Step 2: Multiple imputation by treatment group using linear mixed model regression with factors of baseline pain score, baseline HbA1c, gender, and age will be applied to the data

obtained from the MCMC step. The imputed score will be rounded to the first decimal point.

The entire procedure will be repeated 10 times, and 10 complete datasets will be used for the analysis.

Mean of the other group (MOTH):⁴

- 1. For a participant with missing average pain score/the worst pain score in the full BPI-DPN instrument from the 7 days prior to the Day 0 to Day 90, and Day 180 visits, identify the participant's following baseline characteristics:
 - Study treatment group
 - o Baseline Average Daily Pain Score (<median or ≥median)
 - HbA1c (<median or ≥median)
 - o Gender (male or female)
 - Age (<65 years and ≥65 years)
- 2. The missing mean pain score from the 7 days prior to the Day 0, Day 90, and Day 180 visits will be imputed by using the mean pain score obtained at the same time point of those participants in the other treatment group who match the participant's baseline characteristics. For example, for the missing pain scores of the Engensis participants, the mean pain scores of the placebo participants within the same covariate groups will be used to impute the missing pain scores.
- 3. The baseline characteristics will be re-examined for appropriateness and may be re-categorized (due to small sample size) before unblinding the study.
- 4. The imputed score will be rounded to the first decimal point. The imputed scores will be included in the continuous Repeated Measures Model (Section 8.4.1) analysis.

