### 9.1. Sample Size Determination

The sample size for the primary efficacy endpoint is calculated based on the hypothesis for the primary efficacy endpoints.

The primary efficacy endpoint is the change in the mean ADPS recorded at the Day 0 and Day 180 Visits obtained from 5 to 7 daily entries in the BPI-DPN eDiary prior to those Visits.

The statistical hypothesis for the primary efficacy endpoint (Hypothesis I) is:

$$H_0: \mu_t = \mu_p \text{ versus } H_a: \mu_t \neq \mu_p, (I)$$

where  $\mu_t$  and  $\mu_p$  are the mean pain change from Baseline to 6-month follow-up for the Engensis and Placebo groups, respectively. A negative mean value means a reduction in the pain score, and a positive mean value means an increase in the pain score. The statistical power is 80%.

Details on the assumptions for sample size determination are described in the Statistical Analysis Plan.

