5. SAMPLE SIZE CALCULATION

The sample size for this clinical investigation was based on the primary efficacy endpoint. Based on the VMDN-002 and VMDN-003b findings, the standard deviation of the pain score change from baseline is assumed to be 2.18. Table 3 provides the summary statistics for the corresponding efficacy endpoints based on change in the Average Daily Pain Score for the low- dose and placebo groups from the ITT population and efficacy population in the VMDN-002 trial as well as the mean and standard deviation of change from baseline in the ITT population in the VMDN-003b trial.

Table 3: Mean and Standard Deviation of Pain Score Changes from Baseline in VMDN-002 and VMDN-003b Trials

Trial (Population)	Placebo	Engensis	Mean Difference	Placebo STD	VM202 STD	Pooled STD
VMDN-002 (ITT population)	-1.63	-2.58	0.95	1.76	2.19	2.08
VMDN-002 (Efficacy population)	-1.59	-2.78	1.19	1.89	2.24	2.18
VMDN-003b (ITT population)	-1.49	-2.52	1.03	1.77	2.23	2.13

Abbreviations: ITT, intent-to-treat; STD, standard deviation.

The estimates presented in Table 4 consider a range of scenarios. Following a careful review, the maximum sample size is 250 participants. The target sample size is 152 participants and is based on the following assumptions:

- Mean difference between active and control of 1 point
- Common standard deviation of 2.18 units
- Randomization ratio: 1:1
- 2-sided test with a type 1 error rate of 5%

Table 4: Sample Size Scenarios

Scenario	Primary Endpoint Mean Difference (Engensis minus Placebo)	Nominal Power	Actual Power	Total Sample Size
1	-1	80%	0.802	152
2	-1	85%	0.853	174
3	-1	90%	0.900	202
4	-1	95%	0.951	250
5	-1.2	80%	0.802	106
6	-1.2	85%	0.854	122
7	-1.2	90%	0.903	142
8	-1.2	95%	0.951	174

VMDN-003-2 Version 7.0

When 50% of the minimum target sample size (76 subjects) has been enrolled and completed or withdrawn prematurely, a re-estimation of the sample size based on the conditional power will be conducted based on the method described by Mehta and Pocock.²

The maximum sample size of 250 will provide 95% power for the treatment difference of 1.0 point when other assumptions are held the same. Simultaneously, the maximum sample size of 250 is considered an appropriate sample size to claim statistical significance for the clinically meaningful difference with an effect size of \geq 0.3.

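### Ten imputations leave seed-dependent Monte Carlo error in the p-value: assuming 10–20% missing Day 180 scores at N=152, two runs give opposite verdicts at 0.05 in about 3–7% of trials

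*SAP*

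**What the plan says.** SAP 7.6.1 treats the mean pain score for a visit as missing, "considered as missing if fewer than 5 of 7 days of BPI-DPN eDiary entries are provided", and then imputes it. Two methods are listed.

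- **Multiple imputation.** Intermittent gaps are filled by MCMC within arm to give a monotone pattern. The second step is "Multiple imputation by treatment group using linear mixed model regression with factors of baseline pain score, baseline HbA1c, gender, and age". On the number of imputations: "The entire procedure will be repeated 10 times, and 10 complete datasets will be used for the analysis".
- **Mean of the other group (MOTH).** A missing score is replaced by the mean of matched participants in the opposite arm.

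The readable text does not rank the two methods. Its one explicit link to the repeated measures model of Section 8.4.1 is in the MOTH list. The text of Sections 8.4.1 to 8.4.6 is not shown. Nothing readable gives a reason for choosing ten, a check of Monte Carlo error or an expected missing-data rate.

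**The concern.** Multiple imputation draws random values, so its p-value varies with the seed. Ten draws keep nearly all the statistical efficiency, but that is a different question from whether the p-value is stable. With planned power of only 80%, a good share of trials with the design effect fall close to the 0.05 boundary, and there a small movement in the test statistic changes the verdict. Two analysts following the same SAP on the same locked data could then report different conclusions.

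SAP 7.4 tests the primary endpoint first and stops at the first non-significant result. If the imputed analysis is the primary one, a flip there also decides whether the two secondary endpoints can be claimed.

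**Working it through.** **Inputs from the documents.** "Mean difference between active and control of 1 point"; "Common standard deviation of 2.18 units"; "2-sided test with a type 1 error rate of 5"%; 1:1 allocation; target N=152, maximum 250 (all SAP Section 5). "The statistical power is 80"% (Protocol 9.1). Number of imputations m = 10 (SAP 7.6.1).

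**Assumed.** Share of Day 180 scores missing: 5–30%, central range 10–20%. Share of outcome variance explained by the covariates: 15–65%.

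**Step 1: the plan's own figure.** A two-sample t-test with 76 per arm, difference 1 and SD 2.18 has power 0.802, as in SAP Table 4, scenario 1. The other seven rows also reproduce.

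**Step 2: simulation at N=152, 1-point effect, m = 10.** Missingness was monotone and completely at random, with half of the dropouts also missing Day 90. Scores were imputed by Bayesian regression within arm on baseline and Day 90, analysed by ANCOVA and combined by Rubin's rules with Barnard–Rubin degrees of freedom. For 5–25% missing there were 3,000 trials per setting and 12 seeds per trial. Ranges run over the covariate assumption.

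| Missing (assumed) | Fraction of missing information | Two runs disagree at 0.05 | One run differs from pooled result |
|---|---|---|---|
| 5% | 0.038–0.054 | 1.7–2.2% | 1.2–1.5% |
| 10% | 0.076–0.108 | 2.8–3.6% | 1.9–2.5% |
| 15% | 0.114–0.159 | 3.7–5.3% | 2.5–3.6% |
| 20% | 0.154–0.212 | 4.7–7.1% | 3.1–4.9% |
| 25% | 0.193–0.264 | 6.1–8.5% | 4.1–5.9% |
| 30% | not tabulated | about 9–10% | not tabulated |

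**Step 3: check by hand.** Write F for the fraction of missing information. The seed-to-seed SD of z near the boundary is about √[F/m + (½ × 1.96 × F × √(2/(m−1)))²]. The first term is the noise in the pooled estimate and the second the noise in its standard error.

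- F = 0.108, m = 10: √(0.0108 + 0.0025) = 0.115
- F = 0.212, m = 10: √(0.0212 + 0.0096) = 0.175

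The mean of z is 1/(2.18 × √(2/76)) = 2.83, so its density at 1.96 is φ(0.87) = 0.274. Two runs disagree with probability of about 0.274 × (2/√π) × SD:

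- 0.274 × 1.128 × 0.115 = 3.6%
- 0.274 × 1.128 × 0.175 = 5.4%

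One run against the pooled result uses √(2/π) = 0.798 instead, giving 2.5% and 3.8%. The hand figures at 20% missing fall below the top of the simulated range, in part because they ignore the power lost to missing data.

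**Step 4: other settings, m = 10, 10–20% missing.**

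- N=250, effect 1: 0.8–1.9%
- no effect: 1.0–2.3%
- N=250, effect 0.7: 4–7%
- N=152, effect 0.8: 4–9%

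The density near the boundary explains the pattern. At N=250 with a 1-point effect, z has mean 1/(2.18 × √(2/125)) = 3.63 and density φ(1.67) = 0.10. With no effect the two tails together give 2 × φ(1.96) = 0.117. Both are well under 0.274.

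**Step 5: more imputations (N=152, 1 point, covariates explaining 50% of variance).** Chance that two runs disagree:

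| m | 10% missing | 20% missing |
|---|---|---|
| 10 | 3.0% | 5–6% |
| 20 | 2.0% | 4.3% |
| 50 | 1.6% | 2.4% |
| 100 | 1.0% | 1.1% |
| 200 | 0.6% | 0.5% |

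The hand formula at m = 100 gives SDs of 0.032 (F = 0.086) and 0.048 (F = 0.172), hence 1.0% and 1.5%. A smaller, separate simulation gave 0.3–1.9%. About 1% is a fair summary.

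**The case against.** **Ten is enough.** For validity, it is. Rubin's rules add the between-imputation variance divided by m to the standard error, so intervals and type I error are sound. This stands and limits the point to reproducibility.

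**Comparing two ten-imputation runs counts the noise twice.** This is also fair. The second measure, one run against the pooled result, gives about 2–5% in place of 3–7%.

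**The missing rate is invented.** It is an assumption, and the documents contain measures that lower it. Protocol 8.3.1 reschedules the Day 0 or Day 180 visit when there are fewer than five diary entries, and SAP 7.2 uses diary data even if the visit itself is missed. At 5% missing the disagreement is about 2%.

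**More imputations and a fixed seed do not remove the dependence.** True: a prespecified seed prevents a choice among seeds but leaves the result tied to that seed. Raising m reduces the noise without abolishing it.

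Three stronger readings are tempting, and the documents do not support them:

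- *The ten-imputation p-value decides the primary test.* MOTH is listed alongside it, MOTH involves no random draw, and the Section 8.4.1 text is not shown. Multiple imputation may be primary or a sensitivity analysis.
- *No seed is specified.* It may be given in the unseen Section 8.4 text.
- *Rounding does harm.* The instruction "The imputed score will be rounded to the first decimal point" has no stated purpose. In simulation, however, rounding shifted the p-value by at most 0.001 on average and changed the verdict in at most 0.15% of trials. An effect on the 50% responder cut was not computed, and the readable text does not say that the responder analysis uses these imputed values.

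**Conclusion.** The point holds as a minor, nearly free improvement. Ten imputations give a valid analysis whose verdict near 0.05 depends more on the seed than it needs to. The 3–7% figure (2–5% for a single run against the pooled result) rests on N=152, a true 1-point difference, SD 2.18 and an assumed 10–20% of Day 180 scores missing completely at random. It is not a general rate: Steps 2 and 4 show values from about 1% to about 10%, depending on missingness, sample size and true effect. What it affects depends on the role of multiple imputation, which the readable text leaves open: either the test that opens the hierarchy or a supporting analysis.

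**What to change.** In SAP 7.6.1, change the number of imputations from 10 to at least 100. Prespecify the random seed as well, unless Section 8.4 already does so. The first change reduces the noise; the second removes any question of choosing among seeds. The same edit serves whether the analysis is primary or supportive. The cost is one number, one added line if needed, and a few minutes of computing. No change to the rounding rule is needed on these grounds.
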